 Better and a definite improvement that has made a real and worthwhile difference (6)
 A great deal better and a considerable improvement that has made all the difference (7)

Patient's Signature:_

EORTC QLQ-C15-PAL (version 1)

We are interested in some things about you and your health. Please answer all of the questions yourself by circling the number that best applies to you. There are no "right" or "wrong" answers. The information that you provide will remain strictly confidential.

Ple Yo To	ease fill in your initials:	1			
		Not a All	t A Little	Quite a Bit	Very Much
1.	Do you have any trouble taking a short walk outside of the house?	1	2	3	4
2.	Do you need to stay in bed or a chair during the day?	1	2	3	4
3.	Do you need help with eating, dressing, washing yourself or using the toilet?	1	2	3	4
Dı	ring the past week:	Not a All	t A Little	Quite a Bit	Very Much
4.	Were you short of breath?	1	2	3	4
5.	Have you had pain?	1	2	3	4
6.	Have you had trouble sleeping?	1	2	3	4
7.	Have you felt weak?	1	2	3	4
8.	Have you lacked appetite?	1	2	3	4
9.	Have you felt nauseated?	1	2	3	4

Please go on to the next page

During the past week:	Not at All	A Little	Quite a Bit	Very Much
10. Have you been constipated?	1	2	3	4
11. Were you tired?	1	2	3	4
12. Did pain interfere with your daily activities?	1	2	3	4
13. Did you feel tense?	1	2	3	4
14. Did you feel depressed?	1	2	3	4

For the following question please circle the number between 1 and 7 that best applies to you

15. How would you rate your overall quality of life during the past week?

1 2 3 4 5 6 7

Very poor

Excellent

Date:	
Subject ID:	

Short-form McGill Pain Questionnaire 2 (SF-MPQ-2)

For this questionnaire, I will provide you a list of words that describe some of the different qualities of pain and related symptoms. Please rate the intensity of each of the pain and related symptoms you felt during the past week on 0 to 10 scale, with 0 being no pain and 10 being the worst pain you can imagine. Use 0 if the word does not describe your pain or related symptoms. Limit yourself to a description of the pain related to your surgery or pelvic pain.

1. Throbbing pain	none	0	1	2	3	4	5	6	7	8	9	10	worst possible
2. Shooting pain	none	0	1	2	3	4	5	6	7	8	9	10	worst possible
3. Stabbing pain	none	0	1	2	3	4	5	6	7	8	9	10	worst possible
4. Sharp pain	none	0	1	2	3	4	5	6	7	8	9	10	worst possible
5. Cramping pain	none	0	1	2	3	4	5	6	7	8	9	10	worst possible
6. Gnawing pain	none	0	1	2	3	4	5	6	7	8	9	10	worst possible
7. Hot-burning pain	none	0	1	2	3	4	5	6	7	8	9	10	worst possible
8. Aching pain	none	0	1	2	3	4	5	6	7	8	9	10	worst possible
9. Heavy pain	none	0	1	2	3	4	5	6	7	8	9	10	worst possible
10. Tender	none	0	1	2	3	4	5	6	7	8	9	10	worst possible
11. Splitting pain	none	0	1	2	3	4	5	6	7	8	9	10	worst possible
12. Tiring-exhausting	none	0	1	2	3	4	5	6	7	8	9	10	worst possible
13. Sickening	none	0	1	2	3	4	5	6	7	8	9	10	worst possible
14. Fearful	none	0	1	2	3	4	5	6	7	8	9	10	worst possible
15. Punishing-cruel	none	0	1	2	3	4	5	6	7	8	9	10	worst possible
16. Electric-shock pain	none	0	1	2	3	4	5	6	7	8	9	10	worst possible
17. Cold-freezing pain	none	0	1	2	3	4	5	6	7	8	9	10	worst possible
18. Piercing	none	0	1	2	3	4	5	6	7	8	9	10	worst possible
19. Pain caused by	none	0	1	2	3	4	5	6	7	8	9	10	worst possible
20. Itching	none	0	1	2	3	4	5	6	7	8	9	10	worst possible
21. Tingling or 'pins and needles'	none	0	1	2	3	4	5	6	7	8	9	10	worst possible
22. Numbness	none	0	1	2	3	4	5	6	7	8	9	10	worst possible
23. Present Pain Intensity (PPI) – Numerical Pain Rating Scale. On a scale from zero to ten, zero indicating no pain and ten indicating worst pain imaginable, rate your pelvic pain:													
	None	0	1	2	3	4	5	6	7	8	9	10	worst possible
24. Evaluative overall intensity of total pain experience. Please check ($$) the word that describes the pain in													

your pelvic area only.

D No pain	D Mild	Discomforting	D Distressing	D Horrible	D Excruciating
-----------	--------	---------------	---------------	------------	----------------

Sleep Scale from the Medical Outcomes Study

1. How long did it usually take for you to fall asleep during the past 4 weeks?

(Circle One)

0-15	minutes1
16 - 30	minutes2
31-45	minutes3
46 - 60	minutes4
More	than 60 minutes5

2. On the average, how many hours did you sleep each night during the past 4 weeks?

Write in number	
of hours per night:	

How often during the past 4 weeks did you...

		(Circle One Number On Each Line)								
		All of the Time ▼	Most of the Time ▼	A Good Bit of the Time ▼	Some of the Time ▼	A Little of the Time ▼	None of the Time ▼			
3.	feel that your sleep was not quiet (moving restlessly, feeling tense, speaking, etc., while sleeping)?	1	2	3	4	5	б			
4.	get enough sleep to feel rested upon waking in the morning?	1	2	3	4	5	б			
5.	awaken short of breath or with a headache?	1	2	3	4	5	б			
б.	feel drowsy or sleepy during the day?	1	2	3	4	5	6			
7.	have trouble falling asleep?	1	2	3	4	5	6			
8.	awaken during your sleep time and have trouble falling asleep again?	1	2	3	4	5	б			
9.	have trouble staying awake during the day?	1	2	3	4	5	б			
10	snore during your sleep?	1	2	3	4	5	б			
11	take naps (5 minutes or longer) during the day?	1	2	3	4	5	б			
12	get the amount of sleep you needed?	1	2	3	4	5	б			

Copyright, 1986, RAND

Hays, R. D., & Stewart, A. L. (1992). Sleep measures. In A. L. Stewart & J. E. Ware (eds.), Measuring functioning and well-being: The Medical Outcomes Study approach (pp. 235-259), Durham, NC: Duke University Press.

2.5 Statistical Methods

Initially, a sample size of 20 participants per treatment group (active and sham) was selected to achieve 90% power to find a 20% difference in mean percent change in opioid consumption between the two groups with an estimated standard deviation of 22% and 80% power to detect the same difference with a standard deviation of 19% at a two-sided alpha = 0.05.

Bivariate associations between variables were assessed using statistical methods appropriate for the variable types (Fisher's exact for categorical variables; t-test, ANOVA or non-parametric equivalents for continuous variables). Baseline characteristics (demographics, other morbidities, baseline medication use, pain intensity and quality of life) were compared between the two treatment groups to assess effectiveness of randomization and identify important covariates for multivariable analyses. Associations between demographic variables and primary and secondary endpoints were examined. Sensitivity analyses comparing use of data from all participants with use of participants with complete data only was also performed. Agreement between different measures representing the same variable type (e.g., VAS and SF-MPQ-2) was assessed using correlation analyses.

Multivariable analysis with mixed effect regression models were used to assess the effect of treatment group on the primary and secondary outcomes over repeated measures controlling for potential confounders including opioid dose at baseline and using a group*time interaction term to determine differences in time course by treatment. Similar models were used to assess associations of treatment group with the secondary endpoints. Model fit assessed by Akaike's Information Criteria was used to determine the optimal covariance structure.

All statistical analyses were performed using SAS 9.2 (Cary, North Carolina).

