8.7 Early Withdrawal Visit

- 1. Record any Adverse Experiences/troubleshoot any questions or concerns
- 2. Record changes to concomitant medications.
- 3. Review mobile application for adherence of use.
- 4. Perform and record vital signs.
- 5. Review Mobile Application Pain and Sleep assessment.
- 6. Review documentation of analgesic medication use.
- 7. Perform and record SF-MPQ-2 and Quality of life survey
- 8. Collect Quell/Sham device and delete mobile application from subject's phone
- 9. Administer the PGIC.
- 10. Provide subject with results of any preliminary data analysis pertinent to their involvement in the study.
- 11. Address any remaining question or concerns regarding subject's participation in the study.

9. Data Storage

All data will be transmitted and stored to HIPAA compliant encrypted standards.

Future research:

Subject information will be kept for at least 2 years after completion of this study and up to 20 years for future research that has not yet been planned. Future research using the data will first be approved by Scripps IRB. After 2031, the code that links the sample to the subject's traditionally-identifying information will be destroyed. Related de-identified health information will be kept indefinitely for future research studies at Scripps in secure databases.

10. Statistical Analysis

A biostatistician will perform all data analysis. The sample size (20 participants per group) achieves 80% power to find a 20% (absolute) difference in mean percent change in opioid consumption between the two groups with an estimated standard deviation of mean percent change of 22% and 90% power with an estimated standard deviation of 19% in both groups using a two-sided two-sample t-test with a significance level (alpha) of 0.05.

Descriptive statistics will be calculated for baseline characteristics of both study groups and to assess the effectiveness of the randomization. Repeated measures analysis will be used to assess changes in opioid medication use, pain assessments, and quality of life mesaures over time in the intervention group compared to the control group. Mid study analysis will be conducted with all data amassed around week 6 of all subjects enrolled.

11. Discontinuation and Replacement of Study Participants

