11.2 Replacement of Subjects

Subjects who withdraw from the study treatment will not be replaced, as long some data has been collected from the device. This withdraw will be accounted for in our data analysis. Should subjects withdraw from the study without ever using the device, their device will be collected and they will be replaced with a new participant.

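### SAP 2.5 attaches its two power figures to the wrong standard deviations: power at SD 22% is 80%, not 90%, as the protocol states.

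*SAP*

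**What the plan says.** SAP Section 2.5 reports that "a sample size of 20 participants per treatment group (active and sham) was selected" to give "90% power to find a 20% difference in mean percent change in opioid consumption between the two groups with an estimated standard deviation of 22" percent, together with "80% power to detect the same difference with a standard deviation of 19" percent, "at a two-sided alpha = 0.05".

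Protocol Section 10 (Statistical Analysis) describes the same calculation with the figures the other way round: "The sample size (20 participants per group) achieves 80% power to find a 20% (absolute) difference in mean percent change in opioid consumption" between the groups "with an estimated standard deviation of mean percent change of 22% and 90% power with an estimated standard deviation of 19% in both groups". It names a two-sided two-sample t-test at alpha 0.05.

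On withdrawals, Protocol Section 11.2 states: "Subjects who withdraw from the study treatment will not be replaced, as long some data has been collected from the device". Subjects who leave without ever using the device are replaced. Neither power statement mentions an allowance for loss.

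**The concern.** The two documents share the group size, the target difference, the alpha, the pair of SDs and the pair of power values. They differ only in which power goes with which SD, so one of them is wrong. The SAP is suspect before any calculation, because it claims more power under the noisier assumption.

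What is at stake is how a non-significant result is read. Someone working from the SAP alone would believe that, at the more cautious SD of 22%, the trial had a 10% chance of missing a true 20-point difference. If the protocol is right, that chance is 20%. At SD 19% the error runs the other way: the SAP implies a 20% risk where the protocol implies 10%.

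**Working it through.** **Inputs**

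- n = 20 per group (SAP 2.5; Protocol 10)
- difference in mean percent change, Δ = 20 percentage points (both; the protocol specifies that it is absolute)
- SD σ = 22 or 19 percentage points, equal in both groups (both)
- two-sided alpha 0.05 (both)
- two-sample t-test (Protocol 10)

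**Direction.** The noncentrality parameter is λ = Δ / (σ√(2/n)). With Δ and n fixed, λ falls as σ rises, and power falls with λ. The larger SD must therefore have the lower power.

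**Exact power.** Degrees of freedom are 2n − 2 = 38 and the critical value is t = 2.024. Power = P(|T| > 2.024), where T is noncentral t with 38 df and noncentrality λ. Here √(2/20) = 0.3162.

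- σ = 22: λ = 20 / (22 × 0.3162) = 2.875
- σ = 19: λ = 20 / (19 × 0.3162) = 3.329

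| SD | Protocol 10 | SAP 2.5 | Exact t | Normal approximation |
|---|---|---|---|---|
| 22% | 80% | 90% | 80.0% | Φ(2.875 − 1.960) = 82.0% |
| 19% | 90% | 80% | 90.0% | Φ(3.329 − 1.960) = 91.4% |

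The protocol's figures are reproduced by the exact calculation. Neither SAP figure is.

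**Could another convention rescue the SAP?** A one-sided 0.05 test gives 88.1% at SD 22% (exact t; 89.1% by normal approximation), which is near the SAP's 90%. It also gives 94.8% at SD 19% (95.4% normal), further from the SAP's 80%, and it contradicts the SAP's own two-sided alpha. No single convention yields both SAP figures.

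**Sample size implied by the SAP's claims (exact t).** At SD 22%, 26 per group gives 89.5% and 27 gives 90.6%, so 90% power needs 27 per group. At SD 19%, 80% power needs only 16 per group.

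**Effect of withdrawals.** The documents give no expected loss, so 10% and 20% are assumptions, applied to a simple t-test on the subjects who remain:

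| Evaluable per group | SD 22% | SD 19% |
|---|---|---|
| 20 (no loss) | 80.0% | 90.0% |
| 18 (10% loss) | 75.5% | 86.6% |
| 16 (20% loss) | 70.1% | 82.1% |

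**The case against.** The strongest reply is that this is a clerical transposition in a retrospective sentence. SAP 2.5 is written in the past tense and opens by describing what was initially chosen. The protocol, which sets the design, has the pairing right, and nothing in enrolment, endpoint, model or type I error depends on the SAP sentence. A null result would in any case be judged mainly from the confidence interval and the observed SD. All of this is fair, and it limits the consequence to reporting. It does not make the sentence correct. The SAP offers no new inputs, so it misreports the original calculation, and a reader of the SAP alone has no warning of the conflict.

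A second reply concerns withdrawals. The assumed losses are not in the documents. Section 11.2 says withdrawals will be dealt with in the analysis, and Section 11.1 encourages subjects who stop treatment to complete the remaining visits. The SAP's mixed model can use partial follow-up, adjusts for baseline opioid dose, and is accompanied by a comparison of all participants with complete cases. This also stands in part: counting each withdrawal as wholly lost to a t-test is pessimistic, and the actual power of the mixed model may differ. Those provisions concern analysis, though. They do not change the fact that the quoted power figures assume 20 evaluable subjects per group. The withdrawal point is secondary, and the main error does not depend on it.

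**Conclusion.** The concern holds. The SAP's pairing is impossible as written, and recalculation shows that the protocol is the correct document. The SAP overstates power by 10 points at SD 22% and understates it by 10 points at SD 19%. A transposition is the natural explanation.

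This conclusion rests only on inputs stated in both documents and on the protocol's named test. The ordering argument needs no calculation at all. The choice of 20 per group remains consistent with the protocol's own justification. The reduced-power figures under withdrawal are illustrative: they depend on assumed losses and on a t-test standing in for the planned mixed model.

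**What to change.** Correct the sentence in SAP 2.5 so that 80% power goes with SD 22% and 90% power goes with SD 19%, in agreement with Protocol Section 10. Add that both figures assume 20 evaluable subjects per group under a two-sample t-test, and give the power at the number the sponsor expects to be evaluable, stating the loss rate used.

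The cost is one corrected sentence and one added sentence. The stated power becomes less favourable at SD 22%. Enrolment and the planned analysis are unchanged.

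### SAP 2.5 uses between-arm baseline comparisons to find covariates and leaves the list open, so the primary model is data-dependent and forgoes precision that a fixed prognostic baseline could give

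*SAP*

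**What the plan says.** SAP 2.5 lists a broad candidate pool: "Baseline characteristics (demographics, other morbidities, baseline medication use, pain intensity and quality of life". It says that the arms were compared on these both to check the randomisation and to "identify important covariates for multivariable analyses". The next sentence adds a second look at the data: "Associations between demographic variables and primary and secondary endpoints were examined".

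The models themselves are described this way: "Multivariable analysis with mixed effect regression models were used to assess the effect of treatment group on the primary and secondary outcomes", with repeated measures, a group*time term, and adjustment "controlling for potential confounders including opioid dose at baseline". Baseline opioid dose is the only covariate named. There is no closed list, no threshold for calling a difference important, and no criterion based on prognosis.

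Protocol section 10 (Statistical Analysis) has no such selection step. It plans a repeated measures analysis and names no covariate. Baseline tables serve only to describe the groups and check the randomisation: "Descriptive statistics will be calculated for baseline characteristics of both study groups and to assess the effectiveness of the randomization".

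**The concern.** In a randomised trial, differences between arms at baseline arise by chance. Their size carries no information on whether a variable predicts opioid use, which is what decides whether adjustment helps. A rule that looks for covariates in the between-arm comparison has two effects:

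- It brings in terms that are correlated with treatment in this sample, which widens the standard error of the treatment effect.
- It leaves out a truly prognostic variable whenever that variable happens to be balanced, so its gain in precision is lost.

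The final model also depends on the data, and a reader cannot tell which of several possible adjusted estimates was reported. With 40 subjects, 80% planned power at SD 22, no stated allowance for dropout and no replacement of subjects who withdraw after using the device (Protocol 11.2), there is little margin to give away.

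**Working it through.** **Inputs from the documents.** 20 per arm; 20-point difference in mean percent change; SD 22 (80% power) or 19 (90% power); two-sided alpha 0.05; two-sample t-test (Protocol section 10).

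**Assumptions, not in the documents.** One post-baseline outcome analysed by ANCOVA in place of the mixed model; SD 22 read as the spread left after baseline dose; one further baseline variable with correlation r to the outcome; zero or six unrelated candidates beside it; selection when the baseline arm comparison has p<0.05 or p<0.10.

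**Step 1: the plan's own figure.** Noncentrality = difference / (SD × √(2/n)), with 38 degrees of freedom.

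- SD 22: 20 / (22 × √0.1) = 2.87, power 80.0%.
- SD 19: 20 / (19 × √0.1) = 3.33, power 90.0%.

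The protocol's figures reproduce. The SAP attaches 90% to SD 22 and 80% to SD 19, which does not reproduce. That is a separate matter to reconcile; SD 22 with 80% is used below.

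**Step 2: how often chance imbalance triggers selection.** With k independent candidates and threshold p, the probability of at least one selection is 1 − (1 − p)^k. For k = 7 it is 1 − 0.95^7 = 30% at p<0.05 and 1 − 0.90^7 = 52% at p<0.10, although the arms differ only by chance.

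**Step 3: what a fixed prognostic covariate can give.** Residual SD = SD × √(1 − r²).

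- r = 0.3: 22 × √0.91 = 20.99, power 83.5% (37 df).
- r = 0.5: 22 × √0.75 = 19.05, power 89.8% (37 df).

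These are upper limits, since they ignore the small loss from chance correlation between covariate and arm, and the term for dose.

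**Step 4: simulation with dose in every model, one prognostic baseline and six unrelated candidates.**

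| r | Dose only | Dose + imbalance-selected | Dose + prognostic baseline fixed | Type I error, selected |
|---|---|---|---|---|
| 0.3 | 79% | 76-78% | 81-82% | 4.5-4.7% |
| 0.5 | 79% | 77-78% | 88% | 4.0-4.5% |

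Dose-only power is 79% rather than 80% because dose is given no correlation with the outcome here and still costs one degree of freedom.

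**Step 5: how far this depends on the assumptions.**

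- Without the six unrelated candidates (threshold p<0.05), selection costs nothing: 79.2% against 79.1% for dose only at r = 0.3, and 79.3% against 78.6% at r = 0.5.
- Fixing the covariate gains about 1 point at r = 0.2 and loses about 1 to 1.5 points at r = 0.
- If dose itself has correlation 0.5 with the outcome, dose-only power is about 89%. One further covariate then gives 91-92% (r = 0.3) or 97% (r = 0.5) if fixed, against 89-90% or 90-92% if picked by imbalance at p<0.05 or p<0.20. Type I error when picked is 4.4-4.6% or 3.4-4.1%.
- Without dose in the model, fixing four weak covariates with joint correlation 0.3 gains nothing: 79% fixed, 79% picked, 80% unadjusted. The fix should therefore add one strong baseline, not many.

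**Step 6: which contrast gains.** A baseline value does not change over visits. With balanced data, adding it as a main effect leaves the group*time contrast unchanged. In one simulated data set the group*time estimate (−0.779) and its standard error (1.420) were identical with and without a strongly prognostic baseline; only the group main effect became more precise.

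**The case against.** The strongest reply is that the SAP does not state a pure imbalance rule. Demographics were also examined against the endpoints, which is a look at prognosis, and baseline dose, plausibly the strongest predictor, is already in the model. This stands in part: imbalance is a stated route into the model but not the only possible one. The second route also depends on the data, and it covers demographics only, not pain or quality of life.

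The second reply is that thresholds, candidate counts and correlations are all assumed, and that nothing in the documents shows run-in pain to predict change in opioid use. This stands. It is why the results are given as a range that includes r = 0.

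The third is that the SAP model is a repeated-measures model with a group*time term, where a baseline main effect brings nothing to the interaction. This also stands and limits the gain to the group effect averaged over visits or at a given visit.

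A reader might infer that the selection inflates false positives. The documents do not support that: selection on imbalance alone pushes the error rate below 5%. Inflation would need a choice among models after seeing outcomes. The open list and the endpoint screening leave room for this, but the SAP does not say it was done, and it is not quantified here.

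**Conclusion.** The point holds as a weakness of method. Using baseline comparisons to find covariates has no rationale under randomisation, and the open list leaves the primary model unfixed.

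The power cost is mostly a gain forgone. Selection gives about 76-79% against 79% for dose alone, while one fixed prognostic baseline gives 81-82% at r = 0.3 and 88% at r = 0.5. A reader might infer that the trial falls well short of its planned power because of this rule. It does not: the direct loss is about 1 to 3 points with six unrelated candidates and nil without them. Type I error under selection is about 4-4.7% in the main set-up.

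The direction is secure. The size rests on assumed correlations, thresholds and a single-outcome ANCOVA, and it does not carry over to the group*time test.

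**What to change.** Remove covariate selection by baseline comparison and by endpoint screening from SAP 2.5. Fix the primary model's covariates as baseline (weeks 0-2) daily opioid dose and mean run-in pain intensity from the app. Keep the baseline table descriptive, and report any model with selected covariates only as a sensitivity analysis.

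The SAP is written in the past tense. If the analysis is already done, prespecification cannot be restored. In that case present the fixed-covariate model as the main one, state that it was fixed afterwards, and show the dose-only model beside it.

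The cost is a few sentences of SAP text and one degree of freedom. No new data are needed, because Protocol section 3 already has subjects record pain twice daily and track analgesic use in the two weeks before fitting. If run-in pain turns out not to be prognostic, about 1 point of power is lost.

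### The only missing-data check in the available SAP text, all participants against completers, cannot test robustness to dropout that depends on unrecorded worsening

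*SAP*

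**What the plan says.** SAP 2.5 (Statistical Methods) gives the main analysis: "mixed effect regression models were used to assess the effect of treatment group on the primary and secondary outcomes over repeated measures". The model adjusts for potential confounders, of which only baseline opioid dose is named, and has a group-by-time interaction. The one check relevant to missing data is a sensitivity analysis "comparing use of data from all participants with use of participants with complete data only". The available SAP text does not state the missing-data assumption or the estimation method, does not define complete data, and describes no analysis under MNAR.

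Protocol 11.2 says of subjects who withdraw after using the device: "This withdraw will be accounted for in our data analysis". It gives no method. These subjects are not replaced; those who never used the device are. Protocol 11.1 asks for an early discontinuation visit, encourages attendance at the remaining visits, and has the reason for withdrawal recorded. No described analysis uses those reasons. Protocol section 10 gives no expected dropout rate and no allowance for dropout in the sample size.

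**The concern.** A sensitivity analysis should relax the main analysis's assumption. This one tightens it. A likelihood mixed model on all available records allows dropout to depend on earlier recorded opioid use. Discarding incomplete subjects removes that allowance: the completer result is valid only if dropout is completely at random (MCAR) or depends on nothing beyond the model covariates. Neither analysis covers a subject whose opioid need rises after the last diary record and who leaves for that reason.

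That pattern is plausible here. Protocol section 5 enrols people with metastatic cancer and cancer-related pain on active chemotherapy, and each is followed for 10 weeks. Progression could both end participation and raise opioid use, which is the primary endpoint. If this happens more in one arm, the treatment difference is biased, and the planned comparison does not show by how much.

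**Working it through.** **1. The plan's own figure.** Protocol section 10 states "The sample size (20 participants per group) achieves 80% power to find a 20% (absolute) difference in mean percent change" and pairs the SDs as "percent change of 22% and 90% power with an estimated standard deviation of 19% in both groups". The planned test is a t-test, two-sided, at the 5% level. From the noncentral t distribution with 38 degrees of freedom, power is 80.0% at SD 22 and 90.0% at SD 19, so the Protocol figures reproduce. SAP 2.5 pairs the same powers and SDs the other way round, and that version does not reproduce. This is a separate matter and does not affect the present point. Both SDs are carried below.

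**2. Slack in a result at the target.** Inputs: difference 20 points, n = 20 per arm, two-sided alpha 0.05, t(0.975, 38) = 2.024.

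- SE = SD × √(2/20). At SD 22: 22 × 0.3162 = 6.96.
- Critical difference = 2.024 × 6.96 = 14.08.
- Slack = 20 − 14.08 = 5.92 points.
- At SD 19: SE = 6.01, critical difference = 12.16, slack = 7.84.

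**3. Shift that removes significance.** Suppose a share p of the active arm is unobserved at week 10 and their true percent change is worse by δ than the main model implies, with no such departure in the sham arm. The difference is then overstated by p × δ, and significance goes when δ = slack / p. The shares are assumptions.

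| Active-arm dropout | Subjects of 20 | δ at SD 22 | δ / 22 | δ at SD 19 |
|---|---|---|---|---|
| 10% | 2 | 59.2 | 2.7 SD | 78.4 |
| 15% | 3 | 39.4 | 1.8 SD | 52.2 |
| 20% | 4 | 29.6 | 1.3 SD | 39.2 |
| 30% | 6 | 19.7 | 0.9 SD | 26.1 |

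This uses the planning t-test with SD and SE held fixed. Imputation uncertainty would raise the SE and covariate adjustment could lower it.

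**4. What the planned comparison would show.** A simulation was run under these assumptions: four post-baseline visits, SD 22, correlation 0.7 between adjacent visits with first-order autoregressive decay, logistic dropout without return (slope 0.08 per point), true effect zero. Bias in one arm's week-10 mean comes from 400,000 subjects. The gap (completers minus all data, in the treatment difference) comes from up to 3,000 trials of 20 per arm, with the stated mechanism in the active arm and MCAR dropout at the same rate in the sham arm. Negative means opioid use looks lower than it is. Entries are for 20% / 30% dropout.

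| Dropout depends on | Main model bias | Completer bias | Mean gap | SD of gap | Trials with gap over 5 points in size |
|---|---|---|---|---|---|
| Nothing (MCAR) | about 0 | about 0 | about 0 | 2.3 / 3.1 | 4% / 10% |
| Recorded worsening (MAR) | about 0 | −3.2 / −4.5 | −3.1 / −4.6 | 3.2 / 4.8 | 23% / 41% |
| Unrecorded worsening (MNAR) | −2.7 / −4.0 | −4.5 / −6.5 | −1.8 / −2.4 | 2.6 / 3.4 | 11% / 20% |

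The gap is larger where the main model is sound than where it is biased. Under both non-random mechanisms its mean is no larger than its own SD.

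**The case against.** The strongest defence is that much of the worsening would be recorded. Opioid use is logged daily in the diary and reviewed about every two weeks. The early withdrawal visit (Protocol 8.7) reviews it again, and Protocol 11.1 encourages continued attendance after treatment stops. Earlier opioid use is the model's own repeated outcome, so dropout driven by those records leaves the main model about unbiased while completers drift. This stands. A reader might infer that the check cannot pick up any dropout related to worsening pain or disease. The documents do not support that, because worsening recorded before exit makes the two analyses diverge in expectation. What remains is that the divergence is noisy at 20 per arm and does not separate MAR from MNAR.

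A reader might also infer that both analyses err in the same direction and by the same amount, for example 0.15 × 40 = 6 points. The same direction is what MNAR dropout gave in the simulation; it is not general. Equal size requires dropouts whose recorded histories match those of stayers, and the simulated biases differ (−2.7 against −4.5 at 20% dropout). Six points is also below one SE of the difference (6.96) and needs dropout that differs by arm. No document supplies a dropout rate, mechanism or shift.

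Finally, the MAR status of the main model is inferred, and the statement that there is only one check applies to the SAP text available.

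**Conclusion.** The concern holds in limited form. The plan promises to account for withdrawal, but the only described check assumes more than the model it tests and leaves MNAR dropout unexamined. Agreement between the two analyses should not be read as robustness, and a gap should not be read as evidence of MNAR.

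The consequence depends on the amount of dropout. At SD 22, 10% active-arm dropout would need a shift of 59 points to overturn a 20-point result, which is a remote prospect. At 30% a shift of 20 points, under one planning SD, is enough. These figures assume that only active-arm dropouts depart from the model, that SD and SE stay fixed, and that the observed difference equals the target. They do not show that the trial's result is biased. This is a worthwhile, low-cost improvement and not a flaw that undermines the analysis.

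**What to change.** - State the estimation method and missing-data assumption of the mixed model, and define complete data.
- Keep the completer result as descriptive.
- Add a delta-adjusted (tipping-point) analysis on percent change in opioid use, so that the shift and the outcome share a scale. Use diary data collected after discontinuation where the visits in Protocol 11.1 provide them. Multiply impute the remaining missing values under MAR. Worsen the imputed active-arm values in 10-point steps until the conclusion changes, going to at least 60 points if dropout is near 10%.
- Report the tipping delta with the number of dropouts and their reasons by arm, so that readers can judge whether such a shift is credible.

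The cost is a paragraph in the SAP and a little multiple-imputation code, with no new data collection. SAP 2.5 is written in the past tense. If the data have already been analysed, the addition must be labelled post hoc.
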